## LIST OF ABBREVIATIONS AND RELEVANT DEFINITIONS

ABR	General Assessment and Registration form (ABR form), the application form that is required for submission to the accredited Ethics Committee; in Dutch: Algemeen Beoordelings- en Registratieformulier (ABR-formulier)
ACWO	Advies Commissie Wetenschap en Onderzoek
AE	Adverse Event
App	(smartphone) Application
AR	Adverse Reaction
ASA	American Society of Anaesthesiologists
CCMO	Central Committee on Research Involving Human Subjects; in Dutch: Centrale Commissie Mensgebonden Onderzoek
CV	Curriculum Vitae
GCP	Good Clinical Practice
GDPR	General Data Protection Regulation; in Dutch: Algemene Verordening Gegevensbescherming (AVG)
IC	Informed Consent
NRS	Numerical Rating Scale (for pain)
NVA	Nederlandse vereniging voor Anesthesiologie
METC	Medical research ethics committee (MREC); in Dutch: medisch-ethische toetsingscommissie (METC)
PDNV	Post Discharge Nausea and Vomiting
PDMS	Patient Data and Management System
POP	Post Operative Pain
(S)AE	(Serious) Adverse Event
SPC	Summary of Product Characteristics; in Dutch: officiële productinformatie IB1-tekst
Sponsor	The sponsor is the party that commissions the organisation or performance of the research, for example a pharmaceutical company, academic hospital, scientific organisation or investigator. A party that provides funding for a study but does not commission it is not regarded as the sponsor, but referred to as a subsidising party.
SUSAR	Suspected Unexpected Serious Adverse Reaction
UAVG	Dutch Act on Implementation of the General Data Protection Regulation; in Dutch: Uitvoeringswet AVG
WMO	Medical Research Involving Human Subjects Act; in Dutch: Wet Medisch-wetenschappelijk Onderzoek met Mensen

## SUMMARY

**Rationale:** To date the majority of surgical interventions is performed in day care and patients are being discharged soon after the first critical postoperative period. At home, patients have limited options to contact the hospital in case of severe pain and nausea. We have provided day care surgical patients with a smartphone application for remote monitoring that is configured to self-record postoperative pain and nausea after being discharged from hospital. Furthermore, it provides a messaging service to contact the hospital in case of (severe) pain or nausea. Despite the promising initial patient experiences of such an application, we do not know whether remote monitoring with a smartphone application improves the patient's experience during the recovery period.

**Objective:** To evaluate the experienced quality of recovery after day care surgery between patients provided with a smartphone application for remote monitoring and patients receiving standard of care (no remote monitoring).

**Study design:** (Non-blinded) randomized controlled trial with mixed methods design

**Study population:** Adult patients (aged 18 years or older) scheduled for day care surgery

**Intervention (if applicable):** The intervention group receives the smartphone application for remote monitoring during weekdays from 8 am to 17 pm up to 7 days after surgery. With this application, patients are able to record experienced pain and nausea. In addition, they can send messages to the hospital. Daily monitoring is performed by an anaesthesia professional who will contact the patient in case severe pain or nausea is reported in the app. The control group receives standard of care (with post-discharge verbal and paper instructions).

**Main study parameters/endpoints:** The main study endpoint is the difference between patients using remote monitoring and patients not using remote monitoring in perceived quality of recovery measured with the QoR-15 questionnaire on the 7th day after day care surgery. Secondary endpoints are 1) the overall score on the Quality of Recovery-15 at day 1, 4 and 7 post discharge, 2) the perceived quality of hospital aftercare and 3) experienced psychological effects of remote monitoring during postoperative recovery from day care surgery.

**Nature and extent of the burden and risks associated with participation, benefit and group relatedness:** Participating in this study does not pose any additional risks either for patients allocated to the intervention group with remote monitoring or for patients allocated to the standard of care group. Patients in the remote monitoring group are being asked to use a smartphone application to record pain and nausea daily for up to 7 days post discharge. Recording pain and nausea will take 2 minutes daily. Patients from both groups are being asked to fill in the validated QoR-15 questionnaire one day before admission and on the 1st, 4th and 7th day post discharge and this will take 2.5 minutes. No extra hospital visits, physical examinations or tests are required. Patients in the remote monitoring group could benefit

from participating in the study because they are monitored daily by a healthcare professional. Therefore, severe pain, nausea and possibly other complications can be noticed and managed earlier.

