## 4. TREATMENT OF PATIENTS

### a. Investigational product/treatment

Patients scheduled for day care surgery within 3 weeks after their pre-anaesthesia workup who fit the inclusion criteria and are willing to participate in this study are allocated to either remote monitoring with a smartphone application after discharge (the intervention) or the standard of care without remote monitoring (control). Both groups will have a pre-anaesthesia workup (e.g. online-assessment, telephone assessment or an assessment during a physical visit to the anaesthesia outpatient department) according to the standards of the Dutch association of Anaesthesiologist and Federation of Medical Specialists (18).

During the pre-anaesthesia workup, patients are being notified about the study by an anaesthesiologist, physician assistant or medical assistant. If interested they will receive the study information and a consent letter. Two days before admission a researcher will explain the study during a telephone call and will ask for informed consent. Moreover, participating patients are asked to complete the first online QoR-15 questionnaire.

Patients allocated to the intervention group also receive an invitation e-mail with instructions from Thuismeten (Luscii) © to download and install the remote monitoring application. This invitation is sent by a healthcare professional through a secured connection via the hospitals' patient data management system (e.g. EPIC ©). During the admission patients from both groups receive perioperative anaesthesia care according to standards based on the Guidelines for treatment of the Dutch association of anaesthesiologists (18, 19).

Patients are regularly asked about their postoperative pain and nausea by either nurses or doctors, at least once per perioperative phase (e.g. recovery and day care ward). In case of severe pain, the patient is administered paracetamol, NSAID's, tramadol or opioids. In case of nausea, the patient is administered metoclopramide or granisteron. Both, pain- and nausea treatment is executed by nurses with the aim of making the patient feel comfortable. Postoperative medication is ordered and supervised by the attending anaesthetist.

Before discharge, patients from both groups receive verbal and paper (APPENDIX I: example discharge information OLVG, in Dutch) care- and recovery instructions from a day care ward nurse. In addition, they receive a medication box containing paracetamol,

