### **iii. Other study parameters (if applicable)**

The following patient baseline characteristics are collected: age, sex, smoking status, body mass index, ASA classification, PONV score, preoperative NRS, PONV prophylaxis, previous surgical or anaesthesia related complications, history of (chronic) pain, history of motion sickness, surgical specialism, surgical procedure and classification (e.g. laparoscopic cholecystectomy, minor), anaesthesiology technique (i.e. general or spinal anaesthesia), surgery duration, intraoperative medication, PONV and NRS for pain at recovery ward, PONV and NRS for pain at day care ward, duration of admission

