### **c. Study procedures**

Patients are recruited to participate in this study during their appointment for anaesthesia pre-assessment (e.g. online assessment, telephone assessment or during visiting the anaesthesia outpatient department). An anaesthesiologist, trainee nurse specialist, physician assistant or medical assistant will verbally explain the study. If interested, they receive an information-letter about the study, and an informed consent form (PIF\_IC\_e1\_e2\_QuReMo\_Versie1\_14\_7\_2021).

Patients who are not informed during the preoperative assessment will be contacted afterwards by one of the researchers to explain the study and to ask them to consider participation. If interested, they receive an information-letter about the study, and an informed consent form (PIF\_IC\_e1\_e2\_QuReMo\_Versie1\_14\_7\_2021).

The patients are given a reflection period of at least 48 hours, after that a researcher or medical assistant will contact the patient if they agree to participate. Patients who have been asked to participate are earmarked in the PDMS (e.g. EPIC). A patient who wishes to participate is asked to sign the consent form and bring it on the day of admission. Patients who, forget to bring their consent form are provided a copy, which is then to be signed on the day of admission. Accordingly, both researchers and patients receive a wet ink copy of the consent form.

After receiving informed consent, the researchers will record the baseline characteristics to the Castor EDC database and perform the randomisation procedure. Moreover, no data is recorded that could trace back the identity of the patients. By randomizing, an anonymous study identification number is allocated to the patients. The researchers from the participating hospitals will keep a secured database in which patient hospital number corresponds with the study identification number, stored locally at their own hospital server. Two days before admission patients in the remote monitoring group (intervention group) receive an invitation e-mail from Luscii © sent by a medical assistant from the anaesthesia outpatient department with instructions to download and install the remote monitoring application. Perioperative patients from both the intervention group and the standard of care group receive anaesthesia

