care according to the standards of the Dutch association of anaesthesiologist (18, 19). Intra- and postoperative characteristics and variables will be recorded in Castor EDC by the researchers. Before discharge, patients from both groups receive verbal and paper care and recovery instructions from a day ward nurse. In addition patients receive a medication box with instructions for use, containing paracetamol, naproxen or diclofenac and in case of an intermediate surgical risk for complications also tramadol or an opioid. Once at home, patients in the intervention group can start using the smartphone application for recording pain and nausea and ask additional questions about their recovery. Subsequently an anaesthesia medical assistant will respond appropriately to patients in need following triage and assessment protocol. At day 1, 4 and 7 post discharge patients from both groups receive an online questionnaire (QoR-15). In case patients do not respond, a researcher or a medical assistant will contact the patients from both study arms by telephone to assess the study endpoint questionnaire (f1\_vragenlijst\_QuReMo\_English\_version\_1\_16\_7\_2021 ). Thereafter, endpoint data will be recorded in Castor EDC by one of the researchers.

In addition, patients from the remote monitoring group who have given permission for an interview to assess the quality of communication with app receive a telephone appointment at day 7 postoperative for a 30 minutes semi structured interview with one of the researchers.

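### Conflicting timings for the first QoR-15, consent, randomisation and the app invitation leave open whether the baseline used in the arm-by-time interaction is taken before open allocation

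*Combined protocol and SAP*

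**What the plan says.** The combined protocol and SAP describes the steps before surgery in three places.

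- **Summary (burden paragraph):** "Patients from both groups are being asked to fill in the validated QoR-15 questionnaire one day before admission".
- **Section 4.a:** "Two days before admission a researcher will explain the study during a telephone call and will ask for informed consent". The next sentence adds that "participating patients are asked to complete the first online QoR-15 questionnaire", and the app invitation is mentioned after that.
- **Section 7.c:** "Two days before admission patients in the remote monitoring group (intervention group) receive an invitation e-mail from Luscii". On consent it says "A patient who wishes to participate is asked to sign the consent form and bring it on the day of admission", with a copy to sign that day for those who forget it. On allocation it says "After receiving informed consent, the researchers will record the baseline characteristics to the Castor EDC database and perform the randomisation procedure".

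Section 7.c gives no time for a pre-operative QoR-15; its questionnaire sentence covers follow-up only ("At day 1, 4 and 7 post discharge patients from both groups receive an online questionnaire (QoR-15"). The list in section 7.a.iii ("The following patient baseline characteristics are collected: age, sex, smoking status, body mass index, ASA classification, PONV score, preoperative NRS, PONV prophylaxis", and further items) does not include the QoR-15.

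The trial is non-blinded (section 3). Sections 2 and 7.a.i define the main endpoint as the between-arm difference in QoR-15 on day 7. Section 9.a plans a t-test or Mann-Whitney test. It also plans a random-intercept model with arm, time (before surgery, days 1, 4 and 7), their interaction and hospital. It does not say which model contrast will be reported.

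**The concern.** A baseline is protected by randomisation only if it is collected before patients can know their arm. Here it is a self-reported score in an open trial, and the plan does not fix its place relative to allocation. If a site follows the Summary for the questionnaire and section 7.c for the invitation, intervention patients answer the baseline one day after being invited to install the app.

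The model in section 9.a treats that score as an outcome at the first time level. With categorical time, the day-7 interaction term is the between-arm difference in change from baseline. An arm difference at baseline caused by knowing the allocation could then be read as a treatment effect, or could hide one. A baseline collected after allocation cannot be repaired in the analysis.

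**Working it through.** **1. The timings side by side** (day 0 = admission)

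| Step | Summary | Section 4.a | Section 7.c |
|---|---|---|---|
| Consent | not timed | call on day -2 | form brought on day 0 |
| Baseline QoR-15 | day -1 | linked to day -2 call | not timed |
| Randomisation | not timed | not timed | after consent |
| App invitation | not timed | after the questionnaire in the text | day -2 |

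- *If telephone agreement permits randomisation:* allocation and invitation can happen by day -2. A day -1 baseline then follows open allocation. A day -2 baseline may fall before or after it; the order of sentences in section 4.a is favourable but is not stated as a rule.
- *If the signed form permits randomisation:* allocation falls on day 0, so a day -1 or day -2 baseline precedes it. An invitation sent to one arm only on day -2 is then impossible.

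Neither reading satisfies all the statements and also secures a baseline before allocation.

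**2. The plan's own figure**

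Inputs from the sample size section: difference 8.0, SD 19.1, two-sided alpha 0.05, power 80%.

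- Normal approximation: 2 × (1.960 + 0.842)² × 19.1² / 8.0² = 89.5, so 90 per group.
- Exact noncentral t: 91 per group, power 80.2%. The stated 91 is reproduced.
- Dropout: 182 / (1 − 0.20) = 227.5, so 228 against 230 stated.

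This calculation uses no baseline.

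**3. How a baseline shift enters the model**

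Let b be the shift in the intervention arm's pre-surgery score from knowing the arm, f the share of it still present on day 7, and δ the day-7 difference without it. With complete data and categorical time:

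- day-7 arm difference = δ + f·b
- day-7 interaction = (δ + f·b) − b = δ − (1 − f)·b

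If the shift is transient (f = 0), the interaction is δ − b and the day-7 difference is δ. One point is 1/8.0 = 12.5% of the target. If it persists equally (f = 1), the interaction is δ and the day-7 difference is δ + b.

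A simulation of the section 9.a model (60 paired runs, correlation 0.5, transient case) agrees: shifts of −1, +1 and +2 moved the day-7 interaction by +1.00, −1.00 and −2.00, and the day-7 arm difference by 0.00.

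**4. Illustration, transient case only**

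Assumed: 91 per arm, SD 19.1 at every time, complete data, equal correlation ρ between times, shift gone by days 1, 4 and 7. The documents give neither ρ nor b.

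SE of the change contrast = 19.1 × √(2(1 − ρ)) × √(2/91). The joint test uses a noncentral F with 3 and 540 df and noncentrality 0.75·b² / (2 × 19.1² × (1 − ρ)/91).

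| | ρ = 0.3 | ρ = 0.5 | ρ = 0.7 |
|---|---|---|---|
| SE (points) | 3.35 | 2.83 | 2.19 |
| 1 point in SE units | 0.30 | 0.35 | 0.46 |
| Day-7 interaction rejects, no app effect, 1-point shift | 6.0% | 6.4% | 7.4% |
| same, 2-point shift | 9.1% | 10.8% | 14.8% |
| Joint 3-df interaction rejects, 1-point shift | 5.8% | 6.1% | 6.9% |
| same, 2-point shift | 8.3% | 9.8% | 13.3% |

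The nominal level is 5%. If the shift persists equally at every follow-up time, these interaction tests stay at 5%.

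**The case against.** The strongest reply is that nothing shows a shift exists. Section 1 places the hypothesised benefit in the postoperative recovery period, and section 4.a has patients start recording only once they are home. A pre-surgery shift is an assumption, and so is its disappearance by day 7. This stands, and is why the error rates above illustrate one case only.

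A second reply is that the day -1 timing sits in a summary of participant burden, while section 4.a gives a workable sequence. That is fair: a planned post-allocation baseline is not documented. What is documented is a conflict that permits one.

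A third is that the QoR-15's absence from section 7.a.iii means little, because that section lists other parameters and the QoR-15 is the endpoint itself. This also stands, and the point does not rely on that absence.

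A reader might go further and infer that the primary comparison is biased by the baseline. The documents do not support this: the main endpoint is the day-7 difference between arms, and its two-sample test uses no pre-surgery score. A reader might also take the day-7 difference to be immune to open-label reporting. It is free of the baseline value, but it would carry any shift that persists to day 7.

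**Conclusion.** The concern holds as a conflict of timing with a limited analytic consequence. The Summary, section 4.a and section 7.c need to be reconciled whatever the size of any bias, because a site cannot follow all three.

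The statistical exposure is confined to the arm-by-time interaction, or equivalently the change from baseline. Each point of pre-surgery shift that has gone by day 7 moves the day-7 interaction by 1 point in the opposite direction; a shift that persists equally moves it by nothing. Size, direction and persistence cannot be taken from the documents.

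The day-7 t-test or Mann-Whitney test, the day-7 contrast from the mixed model (complete data, categorical time) and the 91 per group do not depend on the baseline. Importance is minor to moderate. It would increase only if the interaction term were reported as the main result, which section 9.a neither says nor rules out.

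**What to change.** 1. In the Summary and sections 4.a and 7.c, state one order: consent; baseline QoR-15 requested and time-stamped within a stated pre-admission window; randomisation in Castor; app invitation.
2. In section 7.c, say whether telephone agreement or the signed form is the consent that permits randomisation, and make the invitation day consistent with it.
3. Allow patients without a baseline to be randomised. Handle the missing score under the missing-data section (9.d), and do not collect it after allocation. Making a submitted baseline a condition of randomisation is not needed: it would exclude patients who can contribute fully to the day-7 test.
4. In section 9.a, name the day-7 arm difference, as defined in sections 2 and 7.a.i, as the mixed-model contrast for the main endpoint.

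Step 4 alone keeps the main model estimate independent of the baseline value. Steps 1 to 3 are needed if the interaction is also to be interpreted. The cost is wording in four places, a time stamp in the eCRF, and a slightly earlier call and questionnaire for some patients. The sample size does not change.

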## 1. INTRODUCTION AND RATIONALE

To date the majority of patients receiving minor or intermediate surgical interventions are being discharged as soon as the critical post-operative phase is passed and vital signs and physical wellbeing have been stabilized. In general patients will leave the hospital within 4 to 5 hours after the intervention usually without further monitoring (1). Most hospitals provide their patients with verbal and paper instructions on what to do in case of severe pain, nausea and alleged surgical complications. The usual advice is to contact the surgical or anesthesia outpatient department during office hours and if not available, patients are advised to contact their general practitioner or the hospitals' emergency department. For patients whilst being in pain, nauseous or worried about physical wellbeing, contacting the hospital can be a challenging task. Answering machines and gatekeepers (e.g., secretaries who may or may not connect you with the doctor) stand between the patient and their healthcare professional in order to prevent for improper contact. In addition, doctors and nurses have ongoing clinical obligations, which makes it unrealistic to expect that they are available on-demand.

Maintaining and improving high quality and cost-effective healthcare for outpatients is a hospital priority. The volume and complexity of outpatient surgical procedures continues to increase, with a wider range of patients now considered suitable for day care surgery (2). In-addition, recent drives to reduce the length of hospital stay because of the Covid-19 pandemic emphasize that day care surgery is fundamental to modern patientcare. For example, in the Netherlands in 2012, 54% of the patients are treated via day care surgery versus 25% in 1993 (3), considering 1.4 million surgical procedures annually (4). To realize the aims of improving recovery after outpatient surgery, it is especially important to optimize management of postoperative pain (POP) and post discharge nausea and vomiting (PDNV). Even today, 40% to 75% of the patients experience moderate-to-severe POP (5, 6) and 28% to 57% experience PDNV (7-10).

eHealth interventions are currently broadly applied in perioperative care (e.g. remote monitoring, educational websites and tele-rehabilitation) (11, 12). In a similar way, we configured an existing and already applied remote monitoring application to enable follow up of patients after day care surgery with the objective to improve the efficiency and quality of postoperative recovery. In order to do so, we have provided patients a smartphone application to record postoperative pain and nausea and to be in contact with a healthcare professional when worried about their physical well-being after day-care surgery. Despite the promising first results from a proof of concept study with a similar application amongst

clinically admitted patients we do not know to what extend it improves the patient's recovery after day care surgery (13). A recent systematic review showed that the overall primary purpose of 'pain related' apps is education and pain self-management and to the lesser extend remote monitoring . More importantly, many applications lacked a direct feedback loop between the patient and their healthcare professionals (14, 15).

We hypothesized that the realization of being monitored remotely and receiving feedback from healthcare professionals during the postoperative recovery period will improve patient experienced recovery. In a non-blinded randomized controlled trial with mixed methods design, we propose to answer the following research question: *What is the difference in experienced quality of recovery between patients provided with a smartphone app-based remote monitoring tool and patients without remote monitoring (standard care) after day care surgery?*

